- Results of our study will inform our clinical partners and state policy leaders on their efforts to promote the successful adoption and implementation of the ACEs Aware state policy.

II. Purpose/Objectives/Aims/Research Questions

- This study will test the implementation strategy and examine its impact on the fidelity and reach of ACEs screenings (implementation outcomes), the resulting linkage to support services, and any changes in children's clinical screening scores (i.e., Pediatric Symptoms Checklist) as a result of families being linked to support services.
- The implementation strategy is comprised of the following activities:
 - **Activity 1: Short video-trainings** for clinic personnel (care team staff and providers) on the administration of caregiver-reported screening tools through a trauma-informed care lens and implementation protocols. The trainings will complement the current state-sponsored 2-hour on-line provider training and related trainings currently implemented at the FQHC.
 - **Activity 2: Technical implementation support** using a combined approach comprised of external academic consultants and internal FQHC personnel to increase its internal capacity. Each clinic will receive intense implementation support from the FQHC implementation coach (about 1 hour

per week virtual or in person in the first 10-week trial crossover period), and less intense support in the succeeding 10-week periods (45-60 minutes every other week visit and phone consult). In addition, the Trauma Informed Care (TIC) workgroup, comprised of FQHC leadership (i.e., clinical and quality departments), service providers, communications director, information technology (IT) coordinator, and academic collaborators will support clinics.

- **Activity 3: Use of a validated clinical screening tool** — The Pediatric Symptoms Checklist (PSC) is used in pediatric primary care settings to assess behavioral and social/emotional development. For this study, we will use the PSC tool tailored to children ages 0 to 5 years old. The PSC screening tool is needed, as the ACEs screening called PEARLS only assesses ACEs exposure and not mental health needs, which is a common ACEs sequela.

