- **Activity 4: Use of a technology-based tailored screening algorithm** that will be made available to ACEs screeners using computer tablets. The algorithm will be hosted in a HIPAA compliant REDCap (Research Electronic Data Capture) secure web application, hosted at the PI's institution, to facilitate the screening process.
- Examine the value of pairing the delivery of a state policy with an implementation plan tailored to community-based clinics.
- Convene a diverse workgroup comprised of researchers, health care personnel and patients to refine an implementation strategy designed to support the ACEs state screening policy in community-based clinics.
- Pilot test the feasibility, acceptability, fidelity, and reach (i.e., number of ACEs screenings delivered divided by the total number of eligible child visits to their clinic in a 10-week period) of the developed implementation plan.
- Compare changes in child referrals to mental health services, after caregivers' participation in the screenings, between intervention and comparison clinics.
- Compare changes in PSC scores before and after caregivers' participation in the screenings:
Ten weeks after child's initial screening, a member of the study research team will contact a group of caregivers (n=100) on the phone to implement the Pediatric Symptoms checklist (post) and assess any changes from scores obtained during the initial screening at the clinic (pre). The study statistician will randomly select 35 caregivers from each study clinic who participated in the study (the goal is to interview 20 caregivers x 5 clinical sites), and create a separate database in REDCap with the list of selected caregivers and the phone number provided in the consent form. Research study team members will use the list to contact caregivers to schedule phone interviews. We will use this database to track completed interviews, declines, and not being able to contact. The statistician will replenish the list as needed.

III. Participants (sample) (Consistent with iStar sections 10 (expedited and full board) and 22 (for all submission types))

a. Inclusion and exclusion criteria for enrollment:

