 - 4.9.3.b. As part of the screenings for the study, screening staff will use either the Baby Pediatric Symptoms Checklist (BPSC) or the Preschool PSC based on the child's age to help caregivers more accurately identify perceived behavioral and/or emotional concerns they have about their child. Due to low reading levels among some of our participants, the screener will ask caregivers if they prefer the questions to be read to them by the screener.
 - 4.9.3.c. Once the staff has finished conducting the screenings (i.e., PEARLS and the BPSC or PPSC), the physician will come in to conduct the wellness visit as part of routine care. The physician will use the tablet provided by the screening staff with the REDCap database to check ACES-related health conditions from an automated checklist.
 - 4.9.3.d. Based on our REDCap preprogrammed algorithm, which takes the information from the PEARLS, PSC, and the ACES-related health condition checklist, a pop-up box will appear indicating the child's risk level (low/medium/high). If the child's risk level is determined to be high, the physician will be prompted on the tablet to begin a mental-health referral for the child and the caregiver.
 - 4.9.3.e. Screening staff will document when any caregivers decline screenings, or when there is an incomplete screening for any reason.
 - 4.9.3.e.1 Mediators and primary and secondary outcomes will be collected by the co-leads at the FQHC, the PI and the study

coordinator.

- 4.9.3.e.2 During this time period, EMR data will be pulled by the FQHC's data manager and provided to the PI as excel tables and using a password protected and encrypted email. The following data will be collected from REDCap and from the data manager (EHR records): number of eligible child visits, number of PEARLS and BPSC/PPSC screenings and scores, eligible children who are referred to services, child characteristics, and number of mental health referrals.

4.9.3e.3 At the end of each 10-week trial period, the principal investigator and study statistician will meet to review the REDCap system and will follow up with clinical partners to discuss any questions and unexpected data patterns.

4.10 Months 12-30: An online survey with demographic and survey questions on feasibility, acceptability, and implementation leadership and climate measures will be sent out to clinic staff, managers, and primary-care providers using work emails. Follow up interviews will be conducted on the phone.

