- a. Clinics using implementation strategies will have higher rates of mental health referrals compared to their referral rates before implementing the strategies.
- b. Clinics using implementation strategies will have higher rates of mental health referrals than clinics screening for ACEs and as part of the state funded CALQIC project, without the implementation strategies.
- c. Among children screened, ACEs screenings indicating medium and high risk will lead to mental health referrals at higher rates than screenings indicating low risk.
- d. Exploratory: Are there any differences between in the effect of the implementation strategies on referrals in different sub-groups (such as race, ethnicity, age and gender)?

[figure not shown]
3. Implementation outcomes

- a. Perceive feasibility, acceptability, and usefulness of the intervention will be sufficiently high (see Table 1).

Study design:

Changes to the original study design were needed to accommodate the negative impact that the COVID-19 pandemic had in the partner FQHC system. We conducted a stepped-wedge design (SWD) trial with three sites, with data collection divided into 7 10-week intervals. Study sites remained in the intervention phase for multiple intervals to allow additional data to be collected. In addition to the 3 study sites, 2 additional sites from the same health system served as comparison sites, implementing ACEs screenings without the support of the implementation strategies. See Figure 1 for the SWD schedule.

Figure 1. Stepped-wedge schedule for the ACEs pilot study.

Study sites and patient eligibility:

The study statistician originally selected five clinics from a pool of 16 clinics providing family medicine, pediatric, or primary care for children ages 0 to 5 years old and across five regions to maximize variation (e.g., clinic characteristics such as resources and size). Clinics were located in urban, suburban, rural, and frontier communities. The study PI and FQHC champions invited the identified clinics via email to an informational video session to introduce the study and provided study informational materials to the clinic manager.

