Reach	Measured as a proportion = number of eligible visits in a 10-week period divided by the number of PEARLS and clinical (BPSC/PPSC) screenings. Expect between 80%-92% of eligible children will be screened as threshold; based on pediatric screening studies in primary care. ^{7,8}	EMR system
Mental health referrals	Number of mental health referrals (behavioral analysis, behavioral health, care coordinator, care management, child development/development center or social work) divided by the total # of eligible children in a 10-week trial period. expect 11.4% increased referral rate based on a similar study ⁹ and using current referral rate of 3.8% to inform this threshold [per i2itracks report	EMR system
Changes in BPSC/PPSC	Mean score differences from eligible child visits in each 10-week period. Compare those means in pre vs post implementation periods. No threshold as we will test a two-tail hypothesis for this measure given mixed evidence on the impact of screening policies on access to care and clinical outcomes. ^{10,11} Even if a positive effect is not found, this information is still valuable for implementation and leadership.	EMR system

Measures		
Implementation leadership (ILS)¹²	12-item scale with four subscales measuring proactive leadership, knowledgeable leadership, supportive leadership, and perseverant leadership. Reliability for the total scale is strong ($\alpha=0.98$). An average score of 4+ used as threshold; 5-point Likert scale (not at all-very great extent). Subscale score is based on the mean score for the items; total score is the mean of the subscale scores ¹² ;	Staff provider
Implementation climate¹³	6-item scale measuring the strategic climate for the implementation of interventions. The average interrater agreement: $r^*wg (J) = 0.76$ for the group referenced scale. Items are rated on a 5-item Likert scale (completely disagree-completely agree). Average score of 4+ as threshold ¹³	Staff provider
Covariates		
Child characteristic	Variables include sex, self-identified race and ethnicity, age, language of preference for health care receipt, born in the USA. Note: EMR system does not report data on caregivers of child patients	EMR system

Statistical analysis:

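### Protocol II words the PSC aim as an effect of linkage to services, but the planned 10-week before-after change in a random sample of participants can only be descriptive

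*Protocol*

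**What the plan says.** The purpose statement in Protocol II lists, among the things the study will examine, changes in PSC scores "as a result of families being linked to support services". A later bullet in the same section states the objective differently: "Compare changes in PSC scores before and after caregivers' participation in the screenings".

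That bullet also gives the procedure. A research team member repeats the PSC by phone ten weeks after the child's first screening and compares it with the clinic score. On sampling it says: "The study statistician will randomly select 35 caregivers from each study clinic who participated in the study". On size it says: "the goal is to interview 20 caregivers x 5 clinical sites". Risk level, referral and linkage play no part in the draw.

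Referral is prompted for high-risk results only. In that case, Protocol V.1, step 4.9.3.d, says "the physician will be prompted on the tablet to begin a mental-health referral". The data items in step 4.9.3.e.2 include referrals but nothing on whether a family was actually linked to a service.

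The SAP treats the PSC in another way. In Table 1, the row on changes in BPSC/PPSC averages scores within 10-week periods and compares periods before and after implementation, two-sided and without a threshold. SAP, Data sources, says PSC scores were gathered in REDCap for intervention patients only. SAP, Statistical analysis, gives models for reach and referrals but none for the PSC. The design section adds: "We conducted a stepped-wedge design (SWD) trial with three sites".

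**The concern.** The aim names one exposure, linkage to services, and the procedure measures another, having been screened ten weeks earlier. If few of the sampled children are linked, the mean change mostly describes children who were not. Whatever their number, a single-group change also contains normal development, regression to the mean and the switch from clinic to phone administration.

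What is at stake is the conclusion drawn. A fall in mean score could be reported under the stated purpose as a benefit of services. A flat result could be read as evidence against linkage when the sample could hardly show it. Reach and referrals, the primary outcomes, are not affected.

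**Working it through.** **1. The plan's own sample figure.** 20 caregivers × 5 sites = 100, which reproduces. With the SAP's three sites, 20 × 3 = 60. This is a recruitment target. No SD, effect size or power is given for it, so there is no power calculation to check.

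**2. Inputs for the share referred, all from SAP Table 1.** The current referral rate is 3.8% of eligible children ("using current referral rate of 3.8% to inform this threshold"). The expected figure of 11.4% can be read in three ways:
- a target rate of 11.4%, which equals 3 × 3.8%;
- added percentage points, 3.8 + 11.4 = 15.2%;
- a relative increase, 3.8 × 1.114 = 4.2%.

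Expected reach is 80% to 92%, taken here as screened over eligible, the direction that Protocol II uses.

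**3. Share referred among screened children = rate per eligible child ÷ reach.** This assumes that every referral falls on a screened child. For a given rate and reach it is therefore an upper bound.

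| Reading | Reach 100% | Reach 92% | Reach 80% |
|---|---|---|---|
| Current rate | 3.8% | 4.1% | 4.75% |
| 11.4% relative increase | 4.2% | 4.6% | 5.3% |
| 11.4% as the rate | 11.4% | 12.4% | 14.25% |
| 11.4 added points | 15.2% | 16.5% | 19.0% |

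The range is 3.8% to 19.0%, so 81% to 96% are not referred. In 100 interviews that is 3.8 to 19 referred children. In 60 it is 60 × 0.038 = 2.3 to 60 × 0.19 = 11.4. Even at the 15.2% rate, reach would have to fall below 15.2/50 = 30.4% before a majority of screened children could be referred.

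**4. What the mean change estimates.** Let *p* be the share linked. Then mean change = *p* × (change in linked) + (1 − *p*) × (change in unlinked). With referral standing in for linkage, *p* is 0.038 to 0.19, so 81% to 96% of the weight sits on children who were not referred. An effect confined to the linked children would appear in the overall mean at 4% to 19% of its size. The change in linked children would itself include maturation, regression to the mean and mode of administration, and no concurrent group removes these.

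**5. Whether the SAP's second comparison supplies the missing contrast.** Three places need to be read together:
- Table 1 calls for PSC means from pre-implementation periods.
- Protocol V.1, step 4.8, lists the baseline procedures without the PSC, and Protocol II makes the PSC part of the strategy itself (Activity 3).
- SAP, Data sources, limits PSC scores to intervention patients.

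The documents therefore show no pre-implementation PSC data. The comparison with the non-randomized clinics (Protocol V, Data Analysis) covers screenings and referrals only. Even with earlier scores, a contrast of periods would address the implementation strategy, not linkage.

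**6. What a split by referral status could show.** The detectable difference at 80% power, two-sided 5%, in SDs of change, is (1.96 + 0.84) × √(1/k + 1/(n − k)), where k is the number referred:
- n = 100: 1.47 SD with k = 3.8, and 0.71 SD with k = 19.
- n = 60: 1.89 SD with k = 2.3, and 0.92 SD with k = 11.4.

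Only large differences would be visible.

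**The case against.** The strongest reply is that the plan does not act on the causal phrase. It occurs once, in a general purpose sentence. The operational bullet speaks of change around screening, the SAP has no PSC hypothesis, and the measure is secondary, two-sided and without a threshold. Table 1 accepts in advance that no positive effect may be found. This stands, and it limits the point to what the purpose sentence claims. A reader might infer that the plan will credit any average change to linkage, but no planned analysis does so.

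A reader might also infer that within-child change is the only PSC comparison in the plan. It is not, because Table 1 names the comparison of periods. The trouble there is missing control-period data. Table 1 gives the EMR as source for that row, so if such scores do exist the SAP should say so.

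Third, referral is only a proxy. The documents give no linkage rate, and the sampling frame is consented participants, whose risk may differ from that of all screened children. This also stands. It makes the 4% to 19% an inference. If linkage runs through referral, however, linked children cannot outnumber referred ones.

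Finally, a reader might want to oversample referred children so as to isolate linkage. The documents do not support that. Referral is prompted by a risk level computed partly from the PSC, so referred and non-referred children differ by construction. As an illustration with assumed values, a group 1.5 SD above the mean with a test-retest correlation of 0.6 to 0.9 would appear to improve by 0.15 to 0.6 SD through regression alone, since (1 − r) × 1.5 runs from 0.6 down to 0.15. The same draw also supplies the Aim 2 caregiver interviews, which oversampling would skew. And the SAP describes the trial in the past tense, so a new draw may no longer be possible.

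**Conclusion.** The purpose sentence is wrong as written. The planned PSC follow-up is an uncontrolled 10-week change in randomly drawn participants and cannot attribute change to linkage. On the SAP's figures at least 81% of screened children would not be referred, under every reading of the 11.4% and the expected reach of 80% to 92%. This rests on two assumptions: that referral stands in for linkage, and that consented participants resemble screened children in their referral rate. The lack of a comparator rests on neither.

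A reader might go further and state how far natural drift would outweigh a linkage effect in score points. The documents give neither quantity for the PSC, so no such ratio can be supported. What is affected is the interpretation of a secondary measure.

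**What to change.** In Protocol II, delete "as a result of families being linked to support services". State the objective as a descriptive change in PSC score over the ten weeks after screening, with confidence limits and no attribution to linkage. Report BPSC and PPSC separately, because SAP Table 1 scores the first by subscale and the second by total.

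Reconcile this with the BPSC/PPSC row of SAP Table 1. Either replace the comparison of implementation periods with the within-child change, or identify the pre-implementation PSC data it would use. State the follow-up number that applies to three sites.

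Optionally, add an exploratory summary of change by chart-recorded referral status, adjusted for the initial score and labelled non-causal, in the children already interviewed. Protocol III.b already provides for chart data on referrals.

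The main change costs a few sentences, with no new interviews or data, and can still be made at reporting. The optional summary has low precision (detectable differences of roughly 0.7 to 1.9 SD) and residual confounding by risk.

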Recruitment of caregivers at each clinic for interviews (Aim 2): The caregivers would be informed during initial consent that someone may contact them for a follow up interviews (consent form includes a space to add their phone number for this follow-up contact). A member of our research team will contact selected caregivers to invite them to participate in the follow-up phone interview. Caregivers can decline this follow-up interview at any point. We know caregivers move often or change their phone numbers. We will ask help from the clinic manager in identifying a

current phone number for a caregiver if the one provided in the consent is no longer working. Three attempts will be made to schedule the phone interview with caregivers.

The caregiver consent form will also state that for a group of caregivers selected at random (n=100) they will be contacted 10-weeks after their participation in the study to be asked to follow up questions from the Pediatric Symptoms Checklist (PSC), and about their opinions and experiences with the study, ACEs screening process and suggestions for improvement. Each caregiver will receive a \$50 incentive for participating in the interview. The caregiver consent form also includes language stating that there is a data sharing requirement using a National Data Archive or NDA and per requirement from the federal funding agency.

We will offer the consent form electronically as an option using REDCap to reduce the clinical burden.

From the group of caregivers who are consented at the clinic and who agree to participate in the follow-up interview, the additional recruitment strategies, informed by our clinical partners, are as follows:

- Call caretakers from a local number by obtaining a Google number with each of the clinic's location area code
- The study team members will text caregivers in advance of our interview call so they expect the call. They can reply at that time with "yes" or "no" to confirm. We will add a picture of the flyer.
- Script for the text
 - "Phone call for ACEs interview soon from this number. Text back 'Yes', 'No', or a date to schedule. Flyer attached".

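### The Protocol's 10-week PSC change is an uncontrolled clinic-to-phone comparison among caregivers who could be reached, and no planned analysis addresses non-response or mode in that sample

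*Protocol*

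**What the plan says.** **Objective and procedure.** Protocol section II lists a before-and-after comparison of PSC scores as an objective. Its opening statement of purpose attributes any change to families having been linked to services. The procedure is: "Ten weeks after child's initial screening, a member of the study research team will contact a group of caregivers (n=100) on the phone". The score from the first clinic screening is the pre value. The statistician selects 35 participating caregivers at random per clinic, with a goal of 20 interviews at each of five clinics. A separate REDCap database logs completed interviews, refusals and failed contacts. Then: "The statistician will replenish the list as needed". No order, cap, time limit or denominator is given.

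**Contact.** Protocol section IV.b says of the selected caregivers that "they will be contacted 10-weeks after their participation in the study". It expects telephone numbers to go out of date. "Three attempts will be made to schedule the phone interview with caregivers". It also provides help from clinic managers with current numbers, advance texts, local area codes and a $50 incentive.

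**Mode.** Under Protocol section V.1 (steps 4.9.3.a and b) and V.2, clinic staff conduct the baseline screening on a tablet. Because some caregivers read at a low level, "the screener will ask caregivers if they prefer the questions to be read to them by the screener". Follow-up is by telephone with a member of the research team.

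**Analysis.** The Data Analysis part of Protocol section V has a general comparison of observations with and without missing data, and multiple imputation (10 datasets) as a sensitivity analysis. It does not mention the phone sample. SAP Table 1 defines PSC change as a different quantity: mean visit scores per 10-week period, pre versus post implementation, with the EMR as source. The SAP lists no PSC-change hypothesis and never mentions the phone follow-up. It describes three study sites, not five.

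**The concern.** Three things besides benefit from services can move or misdirect this mean change.

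- **Who is reached.** Only caregivers who answer and agree supply a post score. If their children change differently from the others, the mean is biased for the selected group. If not, non-response only limits whom the result describes. Topping up the list keeps the number of completers near 100 and so hides how many selected caregivers are missing.
- **How the score is taken.** Setting, interviewer and channel all change between pre and post. Any resulting shift passes into the change one for one. It should be largest for caregivers who did not have the items read to them in clinic. The documents do not say whether baseline reading aloud is recorded.
- **Time.** Ten weeks of development and regression to the mean lie inside an uncontrolled change. No window around 10 weeks is stated, nor when replacements are to be called.

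At stake is the interpretation. About 100 completers could be presented as a random sample, and a shift in either direction could be read as a clinical effect of linkage to services.

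**Working it through.** **1. The stated sample.** 20 interviews × 5 clinics = 100, which reproduces the Protocol's figure. The first lists hold 35 × 5 = 175 names, so they suffice on average only if completion is at least 20/35 = 57.1%. That rate is implied; the Protocol does not state it. With the SAP's three sites, 20 × 3 = 60.

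**2. Non-response.** The documents give no completion rate *r*, so a range is assumed. Names needed for 100 interviews are 100/*r*, rounded up. Selected caregivers without a post score are that number minus 100. The chance that one clinic's 35 names give at least 20 interviews is a binomial tail. If reached and unreached caregivers differ by *D* in mean change, the bias is (1 − *r*) × *D*. Here *D* = 0.2 SD of change is assumed.

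| Assumed *r* | Names needed | No post score | Chance 35 names suffice | Bias, SD |
|---|---|---|---|---|
| 30% | 334 | 234 | 0.1% | 0.14 |
| 40% | 250 | 150 | 3% | 0.12 |
| 50% | 200 | 100 | 25% | 0.10 |
| 57.1% | 175 | 75 | 57% | 0.09 |
| 70% | 143 | 43 | 96% | 0.06 |

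With 100 pairs the standard error of the mean change is 1/√100 = 0.10 SD, so the bias in the 40% row is 0.12/0.10 = 1.2 standard errors.

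**3. Does replenishing cause the bias?** Suppose, for illustration, that reachable children improve by 1.5 points, the others by 0, and 40% are reachable. Completing 14 of 35 gives an expected estimate of −1.5. So does completing 20 of 50. The mean over everyone selected is 0.4 × (−1.5) + 0.6 × 0 = −0.6 in both cases. The error of −0.9 comes from non-response; topping up leaves it unchanged and tightens the interval around it.

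**4. Mode or time shift.** Suppose services have no effect and mode or time alone shifts the mean by *m* SD of change. The chance of a significant paired change (normal approximation, two-sided 0.05 assumed because no alpha is stated) is 1 − Φ(1.96 − *m*√n) + Φ(−1.96 − *m*√n).

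| *m* (assumed) | n = 100 | n = 60 |
|---|---|---|
| 0.1 SD | 17% | 12% |
| 0.2 SD | 52% | 34% |
| 0.3 SD | 85% | 64% |

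Here *m* is the average over all completers, so an effect confined to some of them is diluted in proportion to their share.

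For scale, the mean change detectable with 80% power is (1.96 + 0.84)/√n, which is 0.28 SD at n = 100 and 0.36 SD at n = 60.

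**The case against.** The best defence is that the Protocol already does much of what is needed. Selection is random, outcomes of contact are logged, effort goes into reaching people, and a missing-data comparison with imputation is planned. This stands in part: the log makes a proper denominator possible. But no text commits to using it, and the missing-data plan does not say whether a replaced caregiver counts as missing.

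Stronger readings are tempting, and the documents do not support them:

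- A reader might infer that replenishment itself turns a random sample into a biased one. Step 3 of the working shows that it does not.
- A reader might infer that replacements are called late. Both places that give timing say 10 weeks, and replacements could be caregivers just reaching that point. Lateness is possible but not established.
- A reader might infer a switch from self-completion to interview. The baseline is described as conducted by staff, with reading aloud on offer, so the modes partly overlap. What remains is a change of setting, interviewer and channel of unknown size.
- A reader might infer that 20 per clinic is a stopping rule. It is stated as a goal.

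It is also fair to say that the SAP's PSC measure is a different quantity and is untouched by this criticism. That leaves the Protocol's objective without an analysis plan; it does not rescue it.

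**Conclusion.** The point holds for the Protocol's 10-week phone objective. It does not reach the SAP's reach and referral outcomes or its period-mean PSC measure. As planned, the change is uncontrolled, comes from those reached, and mixes a clinic with a phone administration, with no analysis directed at either problem.

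The share of selected caregivers without a follow-up score is 75/175 = 43% at the completion rate the list sizes imply, and 150/250 = 60% if completion is 40%. Whether that biases the mean depends on an unknown difference in change; at an assumed 0.2 SD the bias is 0.09 to 0.12 SD over those two rates. A mode or time shift needs no such condition, and at an assumed 0.2 SD it would produce a significant result about half the time with 100 pairs. The completion rates, *D* and *m* are illustrations: the documents give no completion rate, SD of change or mode effect. This is worth correcting because the Protocol reads the change causally and the main corrections are cheap.

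**What to change.** 1. Count every caregiver ever selected, replacements included, in the denominator, and report completion by clinic from the existing tracking database.
2. Compare baseline PSC, PEARLS, age and language between completers and non-completers. As a sensitivity analysis, give an estimate weighted by inverse response probability, or imputed, with a small covariate set. The SAP's Data sources section places PSC scores and ACEs screening results in REDCap, so the baseline screening data are at hand.
3. State a window around 10 weeks, draw replacements only from caregivers still inside it, and report elapsed time.
4. Record whether the baseline was read aloud, and report the change in that group as a sensitivity analysis.
5. Describe the change as uncontrolled, not as a result of linkage to services. Reconcile it with the SAP's definition and with five versus three clinics (100 versus 60 interviews at 20 per clinic).

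The SAP reports the stepped-wedge trial as already conducted, so items 3 and 4 may come too late. If calls are complete, items 1, 2 and 5 still apply, with elapsed time reported where call dates were kept.

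The cost is modest: one extra field if data collection is still open, some added analysis, and no additional interviews. The weighted estimate will be less precise, and holding replacements to the window may leave fewer than 20 interviews per clinic if response is low.
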